11 ADMINISTRATIVE CONSIDERATIONS

11.1 Investigators and Study Administrative Structure

Before initiation of the study, the Investigators must provide the Sponsor with a completed Form FDA 1572. Study medications may be administered only under the supervision of the Investigators listed on this form. Curriculum vitae must be provided for the Investigators and sub-investigators listed on Form FDA 1572.

The Investigator should ensure that all persons assisting with the study are adequately informed about the protocol, any amendments to the protocol, the study treatments, and their study related duties and functions. The Investigator must maintain a list of sub-investigators and other appropriately qualified persons to whom he or she has delegated significant study related duties.

11.2 Institutional Review Board or Independent Ethics Committee Approval

Before initiation of the study, the Investigator must provide the Sponsor with a copy of the written IRB or IEC approval of the protocol and the informed consent form. This approval must refer to the informed consent form and to the study title, study number, and version and date of issue of the study protocol, as given by the Sponsor on the cover page of the protocol.

Status reports must be submitted to the IRB/IEC at least once per year. The IRB/IEC must be notified of completion of the study. Within 3 months of study completion or termination, a final report must be provided to the IRB/IEC. A copy of these reports will be sent to the study clinical monitor. The Investigators must maintain an accurate and complete record of all submissions made to the IRB/IEC, including a list of all reports and documents submitted. AEs which are reported to the United States FDA or other Regulatory agencies (Investigational New Drug [IND] Safety Reports) must be submitted promptly to the IRB/IEC.

11.3 Ethical Conduct of the Study

The procedures set out in this study protocol, pertaining to the conduct, evaluation, and documentation of this study, are designed to ensure that the Sponsor and Investigators abide by good clinical practice (GCP) as described in the 21 CFR Parts 50, 56, and 312 and the International Conference on Harmonization (ICH) GCP Guidelines.

11.4 Patient Information and Consent

Before enrolling in the clinical study, the patient's parent(s), or the patient's legally authorized representative(s) must consent to participate after the nature, scope, and possible consequences of the clinical study have been explained in a form understandable to him or her. An informed consent form that includes information about the study will be prepared and given to the patient's parent(s), or the patient's legally authorized representative(s). This document will contain all FDA and ICH-required elements.

The informed consent form must be in a language understandable to the patient's parent(s), or the patient's legally authorized representative(s) and must specify who informed the patient's parent(s), or the patient's legally authorized representative.

After reading the informed consent document, the patient, patient's parent(s), or the patient's legally authorized representative(s) must give consent in writing. The patient's consent must be confirmed at the time of consent by the personally dated signature of the patient, patient's parent(s) or the patient's legally authorized representative(s) and by the personally dated signature of the person conducting the informed consent discussions. If the patient, patient's parent(s), or the patient's legally authorized representative(s) is unable to read, oral presentation and explanation of the written informed consent form and information to be supplied must take place in the presence of an impartial witness. Consent (or assent) must be confirmed at the time of consent orally and by the personally dated signature of the patient, patient's parent(s) or by the patient's legally authorized representative(s). The witness and the person conducting the informed consent discussions must also sign and personally date the informed consent document. It should also be recorded and dated in the source document that consent was given.

A copy of the signed and dated consent document(s) must be given to the patient's parent(s), or the patient's legally authorized representative(s). The original signed and dated consent document will be retained by the Investigator.

The Investigator will not undertake any measures specifically required solely for the clinical study until valid consent has been obtained.

A model of the informed consent form to be used in this study will be provided to the sites separately from this protocol.

Where applicable, signed assent(s) to participate in the study must be obtained.

11.5 Patient Confidentiality

Patient names will not be supplied to the Sponsor. Only the patient number and patient initials will be recorded in the eCRF, and if the patient name appears on any other document, it must be obliterated before a copy of the document is supplied to the Sponsor. Study findings stored on a computer will be stored in accordance with local data protection laws. The patients will be told that representatives of the Sponsor, a designated Clinical Research Organization (CRO), the IRB/IEC, or regulatory authorities may inspect their medical records to verify the information collected, and that all personal information made available for inspection will be handled in strictest confidence and in accordance with local data protection laws. The Investigator will maintain a personal patient identification list (patient numbers with the corresponding patient names) to enable records to be identified.

11.6 Study Monitoring

Monitoring procedures that comply with current GCP guidelines will be followed. On-site review of the eCRFs for completeness and clarity, cross-checking with source documents, and clarification of administrative matters will be performed.

The study will be monitored by the Sponsor or its designee. On site monitoring will be performed by a representative of the Sponsor (Clinical Study Monitor) who will review the CRFs and source documents. The site monitor will ensure that the investigation is conducted according to protocol design and regulatory requirements by frequent site visits and communications (letter, telephone, and facsimile).

11.7 Case Report Forms and Study Records

Case report forms are provided for each patient in electronic format. Electronic Data Capture (EDC) will be used for this study. The study data will be recorded from the source documents into the eCRF. The electronic files will be considered as the CRFs.

All forms must be filled out by authorized study personnel. All corrections to the original eCRF entry must indicate the reason for change. The Investigator is required to sign the eCRF after all data have been captured for each patient. If corrections are made after review and signature by the Investigator, he or she must be made aware of the changes, and his or her awareness documented by re-signing the eCRF.

11.7.1 Critical Documents

Before Shire HGT initiates the trial (ie, obtains informed consent [assent if applicable] from the first patient), it is the responsibility of the Investigator to ensure that the following documents are available to Shire HGT or their designee:

- Curricula vitae of Investigator and sub-investigator(s) (current, dated and signed or supported by an official regulatory document)
- Current medical license of Investigator and sub investigator(s)
- Signed and dated agreement of the final protocol
- Signed and dated agreement of any amendment(s), if applicable
- Approval/favorable opinion from the IRB/IEC clearly identifying the documents reviewed: protocol, any amendments, Patient Information/Informed Consent Form (Assent form if applicable), and any other written information to be provided regarding patients recruitment procedures
- Copy of IRB/IEC approved Patient Information/Informed Consent Form (Assent Form if applicable)/any other written information/advertisement
- Any additional regulatory approvals, ie national regulatory approvals
- List of IRB/IEC Committee members/constitution
- Financial agreement(s)
- Documentation from central or local laboratory as applicable
 - Reference ranges
 - Certification/QA scheme/other documentation

Regulatory approval and notification as required must also be available; these are the responsibility of Shire HGT. All trial documents will be available in a Trial Master File (TMF) at the Investigator/trial site and at Shire HGT.

11.8 Data Monitoring Committee

There will be no data monitoring committee for this study.

11.9 Protocol Violations/Deviations

The Investigator will conduct the study in compliance with the protocol. The protocol will not be initiated until the IRB/IEC and the appropriate regulatory authorities have given approval/favorable opinion. Modifications to the protocol will not be made without agreement of the Sponsor. Changes to the protocol will require written IRB/IEC approval/favorable opinion prior to implementation, except when the modification is needed to eliminate an immediate hazard(s) to patients. The IRB/IEC may provide, if applicable regulatory authorities permit, expedited review and approval/favorable opinion for minor change(s) in ongoing studies that have the approval/favorable opinion of the IRB/IEC. The Sponsor will submit all protocol modifications to the regulatory authorities in accordance with the governing regulations. A record of patients screened, but not entered into the study, is also to be maintained. There will be no protocol exemptions granted for this study.

When immediate deviation from the protocol is required to eliminate an immediate hazard(s) to patients, the Investigator will contact the Sponsor or its designee, if circumstances permit, to discuss the planned course of action. Any departures from the protocol must be fully documented as a protocol deviation. Protocol deviations will need to be reviewed by the medical monitor and may also be required to be submitted to the IRB/IEC

Protocol modifications will only be initiated by the Sponsor and must be approved by the IRB/IEC and submitted to the FDA or other applicable international regulatory authority before initiation.

11.10 Access to Source Documentation

Regulatory authorities, the IEC/IRB, or the Sponsor may request access to all source documents, CRFs, and other study documentation for on-site audit or inspection. Direct access to these documents must be guaranteed by the Investigator, who must provide support at all times for these activities. Monitoring and auditing procedures that comply with current GCP guidelines will be followed. On-site review of the CRFs for completeness and clarity, crosschecking with source documents, and clarification of administrative matters will be performed.

11.11 Data Generation and Analysis

The clinical database will be developed and maintained by a contract research organization or an electronic data capture technology provider as designated by Shire HGT. Shire HGT or its designee will be responsible for performing study data management activities.

Adverse events will be coded using MedDRA. Concomitant medication will be coded using WHO-DD. Centralized laboratories will be employed as described in the study manual to aid in consistent measurement of efficacy and safety parameters.

11.12 Premature Closure of the Study

11.12.1 Study Termination

If the Sponsor or an Investigator discovers conditions arising during the study which indicate that the clinical investigation should be halted due to an unacceptable patient risk, the study may be terminated after appropriate consultation between Shire HGT and the Investigators. In addition, a decision on the part of Shire HGT to suspend or discontinue development of the study material may be made at any time.

11.12.2 Site Termination

A specific site may be terminated separate from the general study for, but not limited to, the following conditions:

- The discovery of an unexpected, significant, or unacceptable risk to the patients enrolled at the site.
- Failure of the Investigator to enter patients at an acceptable rate.
- Insufficient adherence by the Investigator to protocol requirements.

11.13 Retention of Data

Essential documents should be retained until at least 2 years after the last approval of a marketing application and until there are no pending or contemplated marketing applications or at least 2 years have elapsed since the formal discontinuation of clinical development of the investigational product. The Sponsor will notify the Investigator if these documents must be retained for a longer period of time. It is the responsibility of the Sponsor to inform the Investigator or institution as to when these documents no longer need to be retained.

Biological samples may be reserved for potential, future, biomarker studies (see Section 7.8.3).

11.14 Financial Disclosure

The Investigator should disclose any financial interests in the Sponsor as described in 21 CFR Part 54 prior to beginning this study. The appropriate form will be provided to the Investigator by the Sponsor, which will be signed and dated by the Investigator, prior to the start of the study.

11.15 Publication and Disclosure Policy

All information concerning the study material, such as patent applications, manufacturing processes, basic scientific data, and formulation information supplied by the Sponsor and not previously published are considered confidential and will remain the sole property of the Sponsor. The Investigator agrees to use this information only in accomplishing this study and will not use it for other purposes.

It is understood by the Investigator that the information developed in the clinical study may be disclosed as required to the authorized regulatory authorities and governmental agencies.

In order to allow for the use of the information derived from the clinical studies, it is understood that there is an obligation to provide the Sponsor with complete test results and all data developed in the study in a timely manner.

The Investigator and any other clinical personnel associated with this study will not publish the results of the study, in whole or in part, at any time, unless they have consulted with Shire HGT, provided Shire HGT a copy of the draft document intended for publication, and obtained Shire HGT's written consent for such publication. All information obtained during the conduct of this study will be regarded as confidential. Shire HGT will use the information for registration purposes and for the general development of the drug.

Appendix 1 Schedule of Events

HGT-SAN-067 Study Assessments for Patients Who Have Received 6 Months of rhHNS Treatment in Study HGT-SAN-055

Assessment	Screening/or HGT-SAN-055 EOS Visit ^k (Month 6 from the start of HGT-SAN-055)	Dosed every 28 (±7) days (ie, Q4W)		Months 12, 24, 36, and 54 (from the start of HGT-SAN-055)	EOS ^f Month 55 (from the start of HGT-SAN-055)	Month 56 Safety Follow-up ^j
		Pre-Tx Day 1 ^a	IT dosing Day 2 (±2)			
Informed Consent/Enrollment		•				
Physical Examination	•	•	•		•	
Height and Weight	•	•			•	
Head Circumference	•			•	•	
Visual and Hearing Assessment				•	•	
ECG	•		• ^b		•	
Vital Signs	•	•	•		•	
Hematology	•	•			•	
Serum Chemistry	•	•			•	
Pregnancy Testing ⁿ	•	•				
Urinalysis	•	•			•	
Leukocyte pellet preparation ^o	•					
Urine Heparan Sulfate and Heparan Sulfate Derivatives	•			• ^c	•	
Plasma and serum Heparan Sulfate and Heparan Sulfate Derivatives	•			• ^c	•	
Anti-rhHNS antibody testing (serum and CSF) ^l	•			•	•	
Auditory Brainstem Response (ABR)	•			•	•	
MRI of the Head	•			•	•	
CSF Sample Collection ^m	•		• ^c		• ^c	
rhHNS dosing: every 28 (±7) days ^{g, d}			•			
Neurological Examination ^h	•	•	•		•	
Full Neurodevelopmental Testing ⁱ	•			•	•	
Children's Sleep Habits Rating Scale	•			•	•	
Child Health Questionnaire-50	•			•	•	
Child Health Questionnaire-87	•			•	•	
Infant Toddler QOL Questionnaire	•			•	•	

HGT-SAN-067 Study Assessments for Patients Who Have Received 6 Months of rhHNS Treatment in Study HGT-SAN-055

Assessment	Screening/or HGT-SAN-055 EOS Visit ^k (Month 6 from the start of HGT-SAN-055)	Dosed every 28 (±7) days (ie, Q4W)		Months 12, 24, 36, and 54 (from the start of HGT-SAN-055)	EOS ^f Month 55 (from the start of HGT-SAN-055)	Month 56 Safety Follow-up ^j
		Pre-Tx Day 1 ^a	IT dosing Day 2 (±2)			
Concomitant Medications, Therapies, and Procedures	•	•	•		•	•
Adverse Event Monitoring	•	•	•		•	•

Abbreviations: ABR = Auditory brainstem response; CSF = cerebrospinal fluid; EOS = end of study ; ECG = electrocardiogram; IT = intrathecal; MRI = Magnetic resonance imaging; TX = treatment

Note: The timing of assessments is calculated from the start of HGT-SAN-055. Therefore, for example, the end-of-study visit, as presented here at Month 54, corresponds to Month 48 in HGT-SAN-067, but represents a total of 54 months of study treatment (48 months in HGT-SAN-067 + 6 months in HGT-SAN-055).

^a Week 1 only, and only performed if >7 days have elapsed since HGT-SAN-055 EOS visit assessments.

^b ECG to be performed following administration of study drug.

^c CSF samples will be obtained according to the process with in the study operations manual). An attempt will be made to obtain a CSF sample via the IDDD prior to each administration of rhHNS and at the End of Study visit. If it is not possible to obtain a CSF using the IDDD, the IDDD may be replaced (up to twice in a 6 month period [including the time in the HGT-SAN-055 study]) or a LP may be performed (can occur up to 5 times in a 6 month period).

^d Patients may be discharged as early as 8 hours post rhHNS infusion (ie, on Day 2) when deemed clinically stable by the Investigator.

^e Specimens collected once a month, at Day 1 of the first treatment week.

^f All patients who complete the study will have end of study assessments performed 30 (±7 days) after their last dose of study drug.

^g If a patient’s IDDD becomes nonfunctional or infected; it will be replaced (up to 2 times in a 6 month period; including the time in Study HGT-SAN-055).

^h The neurological exam should not occur sooner than 4 hours after administration of study drug or before the patient has fully recovered from any anesthesia administered for the dosing, whichever occurs later.

ⁱ Full neurodevelopmental testing includes an assessment with the Vineland Adaptive Behavior Scales, Second Edition (VABS-II)

^j A safety follow up telephone call will be made 30 (±7 days) after End of Study Procedures.

^k Assessments will be required only if more than 60 days have elapsed following the HGT-SAN-055 procedures. These assessments would be repeated within 30 days prior to the first scheduled rhHNS IT dose.

^l Blood sample drawn before IT injection of rhHNS.

^m CSF will be tested for standard chemistries, heparan sulfate and heparan sulfate derivatives, anti-rhHNS antibodies, and MPS exploratory biomarkers.

ⁿ A pregnancy test will be carried out on pre-treatment Day 1 in females who are postmenarche to premenopause (childbearing). The results must be negative before study drug can be administered.

^o A blood sample for leukocyte pellet preparation is to be taken at baseline, before dosing. This pellet should be stored frozen, and will be used for additional disease-related laboratory studies, including possible assessment of cross-reactive immunologic material. If this is not drawn at baseline, it can be drawn at any subsequent visit, but it must be taken before dosing. This only needs to be taken once during the study.

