Enrolled patients will check in to the study center 1 day before each of the scheduled rhHNS dosing days for safety assessments (designated Day 1). If no safety concerns exist, the patient will subsequently receive IT administration of rhHNS on Day 2 (± 2 days). However, if feasible and there are no safety concerns in the opinion of the investigator, the Day 1 and Day 2 assessments may be combined and performed on Day 2; if this is done the results will be recorded as Day 2. Patients will remain in the study centre for at least 8 hours following dosing with rhHNS and will be discharged from the unit when deemed clinically stable by the Investigator.

All patients will have received a series of standardized neurodevelopment assessments; in the HGT-SAN-055 study, these will have occurred at Baseline and either prior to or at the 6-month time point. Patients will continue in HGT-SAN-067 with whichever age specific assessment they began with in HGT-SAN-055. If, however, a patient's capability improves and they become capable of completing assessments at a higher level, such additional assessments may be added. Any additional assessments are to be performed after the original assessments (those used in study HGT-SAN-055) have been carried out.

A MRI of the head and ABR testing will be performed at Months 12, 24, 36, and 54 (note that assessment time point nomenclature includes the 6 months in the HGT-SAN-055 study).

In the event of a device malfunction, X-rays may be performed to investigate, as well as to verify correct catheter and port placement following surgical IDDD implantation or revision. In addition, fluoroscopy may be employed intra-operatively to guide catheter placement. Patients may undergo 3 X-ray examinations in association with each episode of IDDD malfunction and subsequent IDDD revision or replacement. The number of IDDD revisions/replacements is limited to 2 in any 6-month period (including the time in the HGT-SAN-055 study), and the number of protocol-associated X-ray evaluations is limited to 6 exposures in any 6-month period (including time in study HGT-SAN-055).

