Patients will be evaluated for safety throughout the study. Adverse events that occur in HGT-SAN-055 and are ongoing at enrollment in HGT-SAN-067 will be captured as ongoing in the HGT-SAN-055 study and also be reported as a concurrent condition in the HGT-SAN-067 electronic case report forms (eCRFs). Specific safety stopping criteria will be applied and will be based on the types and severity of AEs reported while on-study. These data will be reviewed to inform the decision to discontinue a patient, a dose group, or the study as a whole.

All patients will have an EOS visit 30 (\pm 7) days following their last administration of rhHNS (ie, Month 55). The EOS procedures will include standard clinical laboratory tests (serum chemistry, hematology, and urinalysis) in CSF and blood, protocol specific laboratory testing (eg, anti-rhHNS antibody testing), neurodevelopmental testing, ABR, child health questionnaires, and MRI. Use of concomitant medications, therapies, and procedures will be recorded and AEs will be monitored.

All patients will be contacted by telephone or will have a visit for a Final Safety Follow-up, conducted at 30 (\pm 7) days after the EOS visit (ie, Month 56) to collect updated information on AEs and concomitant medications, therapies, and procedures.

It is anticipated that the IDDD will be used to obtain CSF samples and to deliver administrations of rhHNS. However, if a patient's IDDD appears nonfunctional or if its use is precluded on a scheduled day of dosing, site personnel will refer to protocol [Appendix 3](#) which describes the investigation and management of IDDD-related issues. This will include possible partial revision or complete replacement of the IDDD. A maximum of 2 partial revisions and/or complete replacements are permitted in any 6 month period (including participation in study HGT-SAN-055). If a revision or replacement of the IDDD cannot be scheduled in time to avoid a delay of the next scheduled dose of rhHNS, or if the patient experiences more than 2 IDDD malfunctions in a 6 month period, rhHNS will be administered via LP. Drug may be administered via LP for a maximum of 5 successive monthly doses, after which, IDDD re-implantation or revision must occur.

If there is no significant safety risk in the opinion of the Investigator, a non-functional IDDD may be left in situ for up to 3 months.

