7.9 Anesthesia

Administration of anesthesia/sedation will be given prior to obtaining CSF (when the use of the IDDD is precluded), prior to performing a MRI of the head, the ABR, the CSF opening pressure, and the partial revision or replacement of the IDDD (if applicable).

See [Appendix 1](#) for the Schedule of Events. When logistically feasible, the MRI, ABR, and surgical implantation of the IDDD may be performed together to reduce exposure to general anesthesia.

Note: The neurologic exam and the neurocognitive and developmental assessments must be performed prior to the administration of anesthesia.

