7.10 Audiometry and Auditory Brainstem Response

The rare attenuated patients with MPS IIIA with high levels of cognitive functioning will have hearing tests via clinical audiometry measurement performed using age-appropriate testing methods based on the child's developmental age at the time of the testing. It is anticipated that most of the cognitively-impaired and/or behaviorally-deteriorated patients with Sanfilippo A will be unable to cooperate with a (conscious) hearing evaluation. In these instances, the Investigator will utilize his best clinical judgment to estimate the extent of hearing loss (if any) during the physical examination. In this situation, a specific evaluation of hearing loss will occur during an examination of waveforms in the ABR (see below). If the patient has a history of multiple instances of otitis media or evidence of clinically-significant otitis media on physical examination, which the Investigator believes causes significant conductive hearing loss and impairment of daily living, the Investigator will discuss and offer the parent or legally authorized representative(s) placement of PE tubes as part of the scheduled anesthesia. A patient's PE tubes may be replaced if they fall out during the course of this study.

The ABR will be conducted under anesthesia. The ABR findings will be considered within normal limits if, after applying appropriate correction factors, the waveforms reveal normal morphology.

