7.11 Magnetic Resonance Imaging of the Head

The regional brain volume will be assessed through a MRI, of the head. The patient will be under general anesthesia for this assessment. All MRIs will be centrally read by the University of Minnesota Medical Center. Refer to the Study Operations Manual for specific procedures and precautions.

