8.2.1.1 Day 1 (Pre-treatment) Assessments Performed Prior to Each Dose

- Physical examination
- Height and weight
- Vital signs
- Hematology
- Serum chemistry
- Urinalysis
- Pregnancy testing (applicable females only)
- Neurological examination (performed prior to the administration of anesthesia and the rhHNS IT injection)
- Concomitant medications, therapies, and procedures
- AE assessments

Note: If the HGT-SAN-055 EOS (or HGT-SAN-067 Screening) assessments were performed within 7 days of first intrathecal rhHNS treatment in this study, the pre-treatment assessments described in this section do not need to be completed prior to the first treatment in study HGT-SAN-067.

DAY 1 (PRE-TREATMENT) ADDITIONAL ASSESSMENTS PERFORMED AT MONTHS 12, 24, 36, AND 54

- Head circumference
- Visual and hearing assessments
- Urine heparan sulfate and heparan sulfate derivatives
- Plasma and /or serum heparan sulfate and heparan sulfate derivatives
- Anti-rhHNS antibody testing
- ABR
- MRI of the head
- Full neurodevelopmental testing, including VABS-II (performed prior to the administration of anesthesia and the rhHNS IT injection)
- Children's Sleep Habits Rating Scale
- Child health questionnaire-50
- Child health questionnaire-87
- Infant toddler QOL Questionnaire

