8.2.1.2 Day 2 (± 2 days) Assessments and Administration of rhHNS

Patients may be discharged from the clinical site 8 hours after dosing, if deemed stable by the Investigator.

- Physical examination
- ECG (performed following IT study drug injection)
- Vital signs
- CSF sample collection (obtained prior to IT study drug injection)
- rhHNS IT injection (Day 2 ± 2 days)
- Neurological examination
- Concomitant medications, therapies, and procedures
- AE assessments

The neurological exam should not occur sooner than 4 hours after study drug administration or before the patient has fully recovered from any anesthesia administered for the dosing, whichever occurs later.

8.3 End of Study/Early Termination Procedures: Month 55

Patients who complete the study or who discontinue prior to the end of the study, will have EOS assessments performed 30 (± 7 days) after their last dose of rhHNS.

Patients who discontinue or are withdrawn prior to study completion will be asked to participate in the EOS procedures at the time of discontinuation. Participation in these EOS procedures will be strongly encouraged, but is voluntary for those patients electing to discontinue from the study. Note: Scheduled removal of the IDDD will be required at study completion with sedation or anesthesia, as required.

- Physical examination
- Height and weight
- Head circumference
- Visual and hearing assessment
- ECG
- Vital signs
- Hematology
- Serum chemistries
- Urinalysis
- Urine heparan sulfate and heparan sulfate derivatives
- Plasma and serum heparan sulfate and heparan sulfate derivatives
- Anti-rhHNS antibody testing
- ABR
- MRI of the head
- CSF sample collection
- Neurological examination
- Full neurodevelopmental testing, including VABS-II
- Children's Sleep Habits Rating Scale
- Child health questionnaire-50
- Child health questionnaire-87
- Infant toddler QOL Questionnaire
- Concomitant medications, therapies, and procedures
- AE assessments

All patients who discontinue the study early will have their IDDD removed.

Patients who withdraw or discontinue after having received fewer than 3 IT injections will not need to complete the EOS visit.

Patients who withdraw or discontinue from the study after having received 3 or more IT injections, will be asked to complete the EOS visit and undergo all the scheduled assessments.

8.4 Safety Follow-up (by Telephone or Visit) Month 56

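### Completers are scheduled for MRI and ABR under anesthesia at Month 54 and again about 31 days later at the Month 55 end-of-study visit, with no waiver

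*Protocol*

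**What the plan says.** Section 4.1 (repeated in the Synopsis) states: "A MRI of the head and ABR testing will be performed at Months 12, 24, 36, and 54". Section 8.2.1.1 places these among the "ADDITIONAL ASSESSMENTS PERFORMED AT MONTHS 12, 24, 36, AND 54", on Day 1, before that month's dose. Section 4.1 also puts EOS at Month 55, 30 (±7) days after the last dose, and lists "neurodevelopmental testing, ABR, child health questionnaires, and MRI" among its procedures. Section 8.3 and the EOS column of Appendix 1 agree.

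On anesthesia, Section 7.10 says of the ABR: "The ABR will be conducted under anesthesia". Section 7.11 says of the MRI: "The patient will be under general anesthesia for this assessment". Section 7.9 allows MRI, ABR and device implantation to be combined where logistics permit; they "may be performed together to reduce exposure to general anesthesia". Section 8.3 adds: "Scheduled removal of the IDDD will be required at study completion with sedation or anesthesia, as required".

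At entry, Section 8.1 does not require the screening list, which includes MRI and ABR, to be repeated when less than 60 days separate the HGT-SAN-055 EOS assessments from the start of this study.

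The explanatory note under the Appendix 1 table says that "the end-of-study visit, as presented here at Month 54, corresponds to Month 48 in HGT-SAN-067".

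**The concern.** A child who completes treatment is anesthetized for MRI and ABR at the last dosing visit and again roughly one dosing interval later. The protocol gives no reason for imaging at both points. It treats results of this age as current at entry, but has no matching rule at the end.

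What is at stake is an avoidable anesthetic in a population whose airway risk the protocol itself recognizes: an unacceptably high anesthetic risk is an exclusion criterion in Section 5.3. Against that stands a second imaging point that can add little on change over 4 years, because it differs from the first by about a month and one dose.

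The Appendix 1 note is a smaller, separate matter. It gives the end-of-study label to Month 54, whereas the table above it gives that label to Month 55.

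**Working it through.** **The note's own figure.** 48 months in HGT-SAN-067 + 6 months in HGT-SAN-055 = 54 months. This reproduces and is correct as duration of treatment. The EOS visit at Month 55 is 55 − 6 = Month 49 of HGT-SAN-067. Only the label in the note is wrong.

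**Overlap of the two visits.** The Months 12/24/36/54 column of Appendix 1 has 12 items: head circumference, visual and hearing assessment, urine heparan sulfate, plasma and serum heparan sulfate, anti-rhHNS antibody, ABR, MRI, neurodevelopmental testing, sleep scale, CHQ-50, CHQ-87 and ITQOL. All 12 are marked again under EOS and listed in Section 8.3. Two of them, MRI and ABR, are done under anesthesia, and this point concerns only those two.

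**Interval between the two sessions.** Inputs: the Month 54 items fall on Day 1 (Section 8.2.1.1); the dose is on Day 2 (±2 days), so 0 to 3 days after Day 1 because the Day 1 items precede it (Section 8.2.1.2); EOS is 30 (±7) days after the last dose (Section 8.3). This takes the Month 54 dose as the last one, which follows from EOS being at Month 55.

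- Nominal: (2 − 1) + 30 = 31 days.
- Shortest: 0 + 23 = 23 days.
- Longest: 3 + 37 = 40 days.

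The whole range lies below the 60 days that Section 8.1 accepts at entry.

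**Spacing of MRI/ABR within the extension.** Months 12, 24, 36, 54, 55 give gaps of 12, 12, 18 and 1 month.

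**Point in the dosing cycle.** Doses are 28 (±7) days apart (Section 6.2.1), that is 21 to 35 days from dose to dose. The Month 54 session comes 0 to 3 days before its dose, so the time since the previous dose is 21 − 3 = 18 to 35 − 0 = 35 days, nominally 28 − 1 = 27. At EOS it is 23 to 37 days, nominally 30. The ranges largely coincide, and EOS reflects one further dose.

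**Sessions per completer**, if MRI and ABR share a session: 5 as written (Months 12, 24, 36, 54 and EOS). With one end-of-treatment session: 5 − 1 = 4.

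**Waivers.** The 60-day rule in Section 8.1 applies to screening, and the 7-day rule in Section 8.2.1.1 applies to the first dose of the extension. Neither reaches the end of the study.

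**The case against.** A reader might infer from the Appendix 1 note that the protocol contradicts itself on whether MRI and ABR are done once or twice at the end. The documents do not support that. The EOS table header, Section 4.1 and Section 8.3 put EOS at Month 55, and footnote f puts it 30 (±7) days after the last dose. The Synopsis, Section 4.1, Sections 8.2.1.1 and 8.3 taken together, and the Appendix 1 table all schedule MRI and ABR at both visits. The note is an example of how months are counted and schedules no procedure. A site following the protocol would do both sessions.

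It can also be said that a last on-treatment assessment and a separate EOS assessment form a coherent design; that EOS doubles as the early-termination visit and so needs MRI and ABR; and that Section 7.9 encourages combining procedures without limiting how many visits there are. All of this stands. It makes the repeat a design choice rather than an error, but it does not supply a reason for imaging a completer twice within about a month.

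MRI and ABR are secondary endpoints. Dropping them at Month 54 would make the last imaging gap 55 − 36 = 19 months instead of 18, and all imaging after Month 36 would depend on EOS attendance. Section 8.3 makes EOS procedures voluntary for patients who elect to discontinue. That cost is real and belongs in the choice between the two remedies below.

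**Conclusion.** The point holds as an inexpensive improvement in patient safety. Followed as written, the schedule gives each completer two MRI/ABR sessions under anesthesia about 31 days apart (23 to 40), and no rule allows the second to be skipped. Removing one of them loses a near-duplicate imaging point.

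The saving is at most one MRI/ABR session per completer, 5 to 4, assuming that MRI and ABR share a session. A reader might multiply this by the maximum of 12 patients and claim 12 anesthetics avoided. That is only a ceiling. It needs all 12 to enroll and complete, and it shrinks if a Month 54 dose by lumbar puncture requires anesthesia anyway (Section 6.2.4). If the Month 54 session is the one kept, device removal at EOS may still need sedation or anesthesia.

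Nor does the overlap of all 12 items show that the whole EOS battery is redundant. The argument rests on the anesthetic and therefore covers MRI and ABR only. The wrong label in the Appendix 1 note is editorial.

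The text assessed is Amendment 3, dated 28 August 2012. Amendment 2 has the same schedule and note. A later amendment, if there is one, was not available.

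**What to change.** Do the end-of-treatment MRI and ABR once for completers, in one of two ways.

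1. **Preferred:** remove MRI and ABR from Month 54 in the Synopsis, Sections 4.1 and 8.2.1.1 and Appendix 1, and do them at EOS, in the same session as device removal where feasible. Add device removal to the procedures that Section 7.9 allows to be combined. Cost: the final imaging point moves from Month 54 to Month 55, the last gap becomes 19 months, and that point depends on EOS attendance.
2. **Alternative:** keep Month 54 and waive MRI and ABR at EOS when Month 54 results are less than 60 days old, mirroring Section 8.1. This protects the imaging point, but saves less if device removal needs anesthesia at EOS in any case.

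Under either option, keep MRI and ABR at EOS for patients who terminate early. The Month 54 items that need no anesthesia can stay.

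Separately, correct the Appendix 1 note to say that Month 54 is the last dosing month, completing 54 months of treatment, and that EOS is Month 55.

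All of this is amendment wording. No new data are collected, and one near-duplicate imaging point per completer is given up.
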